27 JAN 2021

Participants **MAY** be withdrawn from both, regorafenib and nivolumab, for the following reasons:

- At the specific request of the sponsor and in liaison with the investigator (e.g., obvious non-compliance, safety concerns).
- Discontinuation of study intervention for toxicity should be considered by the Investigator when a participant meets one of the conditions outlined in Section 6.6 or if the Investigator believes that it is in best interest of the participant.
- If a clinically significant electrocardiogram (ECG) finding is identified (including, but not limited to changes from baseline in QT interval corrected using Fridericia's formula (QT interval corrected for heart rate F [QTcF]) after enrollment, the Investigator or qualified designee will determine if the participant can continue in the study and if any change in participant management is needed. This review of the ECG printed at the time of collection must be documented. Any new clinically relevant finding should be reported as an AE.

See the SoA for data to be collected at the time of intervention discontinuation and FU and for any further evaluations that need to be completed.

If the participant withdraws consent for disclosure of future information, the sponsor may retain and continue to use any data collected before such a withdrawal of consent. If a participant withdraws from the study, he/she may request destruction of any samples taken and not tested, and the investigator must document this in the site study records.

7.2 Participant Discontinuation/Withdrawal from the Study

For details on participant discontinuation and withdrawal from the study please refer to section 7.1.

7.3 Lost to FU

A participant will be considered lost to FU if he or she repeatedly fails to return for scheduled visits and is unable to be contacted by the study site.

The following actions must be taken if a participant fails to return to the clinic for a required study visit:

- The site must attempt to contact the participant and reschedule the missed visit as soon as possible and counsel the participant on the importance of maintaining the assigned visit schedule and ascertain whether or not the participant wishes to and/or should continue in the study.
- Before a participant is deemed lost to follow up, the Investigator or designee must make every effort to regain contact with the participant (where possible, 3 telephone calls and, if necessary, a certified letter to the participant's last known mailing address or local equivalent methods). These contact attempts should be documented in the participant's medical record.

Should the participant continue to be unreachable, he/she will be considered lost to FU.

Discontinuation of specific sites or of the study as a whole are handled as part of Section 10.1.

8. Study Assessments and Procedures

- Study procedures and their timing are summarized in the SoA table (Section 1.3). Protocol waivers or exemptions are not allowed (pre-specified exceptions requiring discussion with the Sponsor are not considered protocol waivers).
- Immediate safety concerns should be discussed with the Sponsor immediately upon occurrence or awareness to determine if the participant should continue or discontinue study intervention.
- Adherence to the study design requirements, including those specified in the SoA (Section 1.3), is essential and required for study conduct.
- All screening evaluations must be completed and reviewed to confirm that potential participants meet all eligibility criteria. The Investigator will maintain a screening log to record details of all participants screened and to confirm eligibility or record reasons for screening failure, as applicable.
- Procedures conducted as part of the participant's routine clinical management (e.g., blood count) and obtained before signing of the ICF may be utilized for screening or baseline purposes provided the procedures met the protocol-specified criteria and were performed within the time frame defined in the SoA (Section 1.3).
- In the event of a significant trial-continuity issue (e.g. caused by a pandemic), alternate strategies for participant visits, assessments, medication distribution and monitoring may be implemented by the sponsor or the investigator, as per local health authority / ethics requirements.

8.1 Efficacy Assessments

For HNSCC (IO-naïve), HNSCC (IO-treated), ESCC, PDAC and BTC, RECIST 1.1 (Section 10.6.1) and iRECIST (Section 10.6.2) criteria will be used to determine the efficacy. iRECIST will be used to make treatment-related decisions beyond initial RECIST 1.1 progression.

For GBM/AA, tumor response and efficacy variables will be evaluated using the RANO (Section 10.6.3) and iRANO criteria (Section 10.6.4). iRANO will also be used to make treatment-related decisions beyond initial progression for GBM/AA.

Imaging acquisitions:

The following anatomic coverage is required:

• HNSCC (IO-naïve and IO-treated): At screening, neck, chest, abdominal and pelvic CT with oral and intravenous (IV) contrast. During treatment and follow-up, neck and chest CT with oral and IV contrast should be performed. Abdominal and pelvic scans should be done if disease is present at screening. Otherwise, abdominal and pelvic scans may be done as clinically indicated if disease was absent at screening. For HNSCC, the anatomic coverage for the neck scan should typically include from the base of the skull to the base of the neck. The reconstructed slice thickness for this

anatomic coverage is highly recommended to be ≤ 3 mm. For the CT scans of the chest, abdomen and pelvis, reconstructed slice thickness should be ≤ 5 mm.

- ESCC: Neck, chest, abdominal and pelvic CT with oral and IV contrast.
- PDAC, BTC: CT of chest, abdomen and pelvis with oral and IV contrast.
- GBM/AA: Brain MRI with and without IV gadolinium-based contrast agent.

When intravenous and oral agents are required per protocol, oral contrast agents may be omitted if the requirement for oral contrast administration is inconsistent with local regulations.

HNSCC, ESCC, PDAC, BTC participants with known or suspected CNS tumor lesions should undergo contrast enhanced MRI (preferred)/CT scans of the brain. Participants with new brain metastases on screening scan are excluded. Participants with known CNS tumor lesions on screening scan should have stable lesions for at least 6 weeks, confirmed by comparison to prior brain MRI/CT scans. If CNS lesion stability is confirmed at screening, participants are eligible to undergo study treatment and brain MRI/CT should be repeated at every tumor assessment time point on study. If any participants develop CNS symptoms during the study, brain MRI/CT should be performed if clinically indicated. For all cohorts, the anatomic coverage should further include any other anatomic areas of known or suspected disease at baseline and throughout the study.

The slice thickness for CT and MRI is strongly recommended to be \leq 5mm without gap. MRI should be performed instead of CT when institutional policy does not recommend the use of CT or there is a contraindication to iodinated CT contrast. It is recommended, that when MRI is used instead of CT, MRI of the abdomen and pelvis (and neck, when applicable) should be performed with a gadolinium-based contrast agent. However, the chest should still be assessed with a CT scan (without contrast if contrast allergy exists). MRI of the chest can be performed in extenuating circumstances (e.g. local health regulations).

Whole-body bone scans with both anterior and posterior projection using a technetium-99m phosphonate tracer (methylene diphosphonate [MDP], hydroxymethylene diphosphonate [HMDP], hydroxyethylene diphosphonate [HDP], or 2,3-dicarboxypropane-1,1- diphosphonate [DPD]) will be performed within 28 days prior to the start of study treatment to establish baseline presence or absence of bone lesions for all participants with known bone metastases or clinically suspected of having bone disease. Bone scans should be repeated when CR or PR is identified in the CT/MRI assessments to confirm the absence of new bone lesion(s) disease or when progression in bone is suspected.

For primary brain tumors (GBM/AA), MRI of the brain should be performed with and without a gadolinium-based contrast agent. Recommended sequences are the following: precontrast axial 3D T1, axial T2 fluid-attenuated inversion recovery (FLAIR) and axial diffusion-weighted imaging (DWI); post-contrast sequences are an axial T2 and a 3D T1. Slice thickness should typically be \leq 5mm without a gap (1mm is optimal for 3D T1 and 3mm for T2, FLAIR and DWI).

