- b. Contact IxRS to record the following: **1**. to register the participant who has signed the PI/ICF **2**. the participant is a screening failure (failed to meet the criteria during the screening period), **3**. on D1 of every treatment cycle in order to register the cycle and to ensure the specific participant drug bottles/vials can be provided for dispensing purposes and also in case the participant has discontinued the study treatment (EoT) for any reason.
- c. AJCC classification for HNSCC, ESCC, PDAC, BTC, and, WHO classification for GBM/AA.
- d. Test results need to be available before start of study treatment.
- e. Participants will be followed for intervention-related toxicities until these toxicities resolve, return to baseline or are deemed irreversible. All AEs will be documented for 30 d + 7 d after study treatment discontinuation or 100 d + 14 d after LD of nivolumab, whatever occurs later. After start of subsequent anti-cancer therapy only study intervention-related AEs should be collected. CTCAE v5.0 will be used.
- f. A negative pregnancy test must be available within 24 h before the 1st study treatment administration. Monthly pregnancy testing independent of study treatment dosing should be conducted as per local regulations where applicable.
- g. Need to be performed within 2 days prior to the study treatment administration. For thyroid function tests, results can also be analyzed retrospectively in case the results are not immediately available.
- h. 12-lead ECG to be scheduled at every cycle on D1 until cycle 6, after which ECG can be performed at the discretion of the investigator if clinically indicated.
- i. CT/MRI scans performed prior to the participant signing informed consent can be used as baseline scans if they are not older than 28 days from C1D1 and meet the requirements outlined in Section 8.1. Scans are to be performed every 8 weeks (± 7 d) through Cycle 8 (or until treatment discontinuation, if treatment discontinuation occurs before), afterwards every 12 weeks (± 14 d). See Section 8.1 for further details on the schedule of tumor assessments beyond progression per RECIST 1.1 or RANO criteria. For all participants with known bone metastases or clinically suspected of having bone disease, bone scans will be performed as outlined in Section 8.1. HNSCC, ESCC, PDAC, BTC participants with neurological symptoms and/or known CNS disease must undergo CT/ MRI scans of the brain as outlined in Section 8.1.

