5.2 Exclusion Criteria

Participants are excluded from the study if any of the following criteria apply:

Cohort 1 (HNSCC IO naïve)

- 101 Cohort 1: Histologically confirmed non-squamous, nasopharyngeal, or salivary histology of head and neck cancer, or squamous cell carcinoma that originated from the skin, or of unknown primary origin.
- 102 Cohort 1: More than 3 prior lines of systemic anticancer therapy for recurrent/metastatic cancer
- 103 Cohort 1: Presence of symptomatic central nervous system (CNS) metastases, leptomeningeal metastases or spinal cord compression. Previously treated lesions should be stable for at least 6 weeks prior to study entry.
- 104 Cohort 1: Participants with a condition requiring systemic treatment with either corticosteroids (>10 mg daily prednisone equivalent) or other immunosuppressive medications within 14 days of start of study treatment. Inhaled or topical steroids, and adrenal replacement steroid doses >10 mg daily prednisone equivalent, are permitted in the absence of active autoimmune disease
- 105 Cohort 1: Prior therapy with PD-1/PD-L1 or cytotoxic T-lymphocyte-associated protein 4 (CTLA-4) inhibitors, or any form of immunotherapy to treat cancer.

Cohort 2 (HNSCC IO treated)

- 201 Cohort 2: Histologically confirmed non-squamous, nasopharyngeal, or salivary histology of head and neck cancer, or squamous cell carcinoma that originated from the skin, or of unknown primary origin.
- 202 Cohort 2: More than 3 prior lines of systemic anticancer therapy for recurrent/metastatic cancer

203 Cohort 2: Presence of symptomatic CNS metastases, leptomeningeal metastases or spinal cord compression. Previously treated lesions should be stable for at least 6 weeks prior to study entry.

204 Cohort 2: Participants with a condition requiring systemic treatment with either corticosteroids (>10 mg daily prednisone equivalent) or other immunosuppressive medications within 14 days of start of study treatment. Inhaled or topical steroids, and adrenal replacement steroid doses >10 mg daily prednisone equivalent, are permitted in the absence of active autoimmune disease

205 Cohort 2: More than one prior therapy with PD-1/PD-L1 or CTLA-4 inhibitors, or any other form of immunotherapy to treat cancer.

Cohort 3 (ESCC)

- 301 Cohort 3: More than 1 prior line of systemic anticancer therapy for recurrent/metastatic cancer

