- 302 Cohort 3: Patients with apparent tumor invasion on organs located adjacent to the esophageal disease (e.g., the aorta or respiratory tract).
- 303 Cohort 3: Patients who have previously received taxane agents for recurrent/metastatic cancer.
- 304 Cohort 3: Presence of symptomatic CNS metastases, leptomeningeal metastases or spinal cord compression. Previously treated lesions should be stable for at least 6 weeks prior to study entry.
- 305 Cohort 3: Participants with a condition requiring systemic treatment with either corticosteroids (>10 mg daily prednisone equivalent) or other immunosuppressive medications within 14 days of start of study treatment. Inhaled or topical steroids, and adrenal replacement steroid doses >10 mg daily prednisone equivalent, are permitted in the absence of active autoimmune disease
- 306 Cohort 3: Prior therapy with PD-1/PD-L1 or CTLA-4 inhibitors, or any form of immunotherapy to treat cancer.

Cohort 4 (PDAC)

- 401 Cohort 4: More than 2 prior lines of systemic anticancer therapy for recurrent/metastatic cancer
- 402 Cohort 4: Presence of symptomatic CNS metastases, leptomeningeal metastases or spinal cord compression. Previously treated lesions should be stable for at least 6 weeks prior to study entry.
- 403 Cohort 4: Participants with a condition requiring systemic treatment with either corticosteroids (>10 mg daily prednisone equivalent) or other immunosuppressive medications within 14 days of start of study treatment. Inhaled or topical steroids, and adrenal replacement steroid doses >10 mg daily prednisone equivalent, are permitted in the absence of active autoimmune disease
- 404 Cohort 4: Prior therapy with PD-1/PD-L1 or CTLA-4 inhibitors, or any form of immunotherapy to treat cancer.

Cohort 5 (BTC)

- 501 Cohort 5: More than 2 prior lines of systemic anticancer therapy for recurrent/metastatic cancer
- 502 Cohort 5: Presence of symptomatic CNS metastases, leptomeningeal metastases or spinal cord compression. Previously treated lesions should be stable for at least 6 weeks prior to study entry.
- 503 Cohort 5: Participants with a condition requiring systemic treatment with either corticosteroids (>10 mg daily prednisone equivalent) or other immunosuppressive medications within 14 days of start of study treatment. Inhaled or topical steroids, and adrenal replacement steroid doses >10 mg daily prednisone equivalent, are permitted in the absence of active autoimmune disease

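### In Cohorts 1–5, the CNS eligibility rules in Protocol Section 8.1 do not match the Section 5.2 exclusions, so three types of patient get a different answer depending on the section read

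*Protocol*

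**What the plan says.** **Section 5.2, Exclusion Criteria.** Exclusions 103, 203, 304, 402 and 502 carry the same criterion for Cohorts 1 to 5. In exclusion 203 it reads, but for its last word, "Presence of symptomatic CNS metastases, leptomeningeal metastases or spinal cord compression. Previously treated lesions should be stable for at least 6 weeks prior to study". The first sentence turns on symptoms, apart from leptomeningeal disease and cord compression. The second turns on prior treatment. No criterion in Section 5.2, whether cohort-specific or for all cohorts, names new or untreated asymptomatic brain metastases, and none refers to Section 8.1.

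**Section 8.1, Imaging acquisitions.** For the same five cohorts, three further statements bear on eligibility:
- On lesions not seen before, the text is "Participants with new brain metastases on screening scan are excluded".
- On lesions already known, which are to be judged against earlier brain imaging, it is "Participants with known CNS tumor lesions on screening scan should have stable lesions for at least 6 weeks".
- On what follows once that has been shown, it is "If CNS lesion stability is confirmed at screening, participants are eligible to undergo study treatment".

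None of the three mentions symptoms or prior treatment.

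**When the brain is scanned.** Section 8.1 says "HNSCC, ESCC, PDAC, BTC participants with known or suspected CNS tumor lesions should undergo contrast enhanced MRI (preferred)/CT scans of the brain". Footnote i of the Schedule of Activities says "participants with neurological symptoms and/or known CNS disease must undergo CT/ MRI scans of the brain" and refers to Section 8.1 for the details.

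**Where sites are sent.** In the Schedule of Activities, the row for inclusion and exclusion criteria points to Section 5. The brain-scan row points to Section 8.1.

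**The concern.** Eligibility is normally checked against the numbered criteria, and the schedule sends sites to Section 5 for that check. A separate set of CNS conditions sits in a paragraph on how to acquire images. A site that screens from Section 5.2 alone could enrol a patient whom Section 8.1 excludes. Another site that reads both could turn the same patient away.

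Three things are at stake:
- **Who is treated.** Whether a patient with a newly found or not-shown-stable asymptomatic brain lesion enters the trial should not depend on the section consulted. This is an eligibility rule with a bearing on safety.
- **Deviations.** Section 5 permits no waivers of enrolment criteria. A patient who passes Section 5.2 and fails Section 8.1 is or is not an eligibility deviation depending on which text governs.
- **Screen-failure records.** Section 5.4 asks for the criterion that was failed. A patient turned away only because of Section 8.1 has no matching CNS criterion in Section 5.2 to record.

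**Working it through.** The plan gives no figure to reproduce here. The check sets the two sections side by side by type of lesion, for Cohorts 1 to 5, assuming no leptomeningeal disease or cord compression.

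| Case | Section 5.2 | Section 8.1 | Agree? |
|---|---|---|---|
| (a) Asymptomatic, new on screening scan | Not excluded | Excluded | No |
| (b) Asymptomatic, known, untreated, not shown stable for 6 weeks | Not excluded | Stability condition not met | No |
| (c) Asymptomatic, known, untreated, shown stable for 6 weeks | Not excluded | Eligible | Yes |
| (d) Asymptomatic, known, treated | 6-week stability asked for | 6-week stability asked for, against a prior scan | Yes, on duration |
| (e) Symptomatic, known, shown stable for 6 weeks | Excluded | Called eligible | No |

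Cases (a) and (b) differ in one direction: Section 8.1 is the stricter. Case (e) differs in the other: Section 5.2 is the stricter.

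**Timing.** Section 8.1 places baseline tumour imaging within 28 days before C1D1. Six weeks is 6 × 7 = 42 days. Since 28 < 42, a lesion whose only scan is the baseline scan cannot show the required stability by C1D1. Section 8.1 therefore cannot be satisfied for any lesion without an earlier scan, whether or not it causes symptoms.

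**Population under the wording.** Planned cohort sizes from Section 9.2 are HNSCC IO-naïve 30, HNSCC IO-treated 20, ESCC 30, PDAC 45, BTC 45 and GBM/AA 30.
- All cohorts: 30 + 20 + 30 + 45 + 45 + 30 = 200.
- Cohorts 1 to 5: 200 − 30 = 170.

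So 170 of 200 planned participants fall in cohorts that carry both texts. The number in cases (a), (b) or (e) cannot be derived, because neither document gives a rate of CNS metastases.

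**The case against.** **Silence is not permission.** Section 5.2 lists reasons to exclude. It does not declare new or untreated asymptomatic metastases eligible. For cases (a) and (b) a site can comply with both sections by applying both, so this can be seen as a misplaced criterion and not as two incompatible rules. That is a fair reading, and for those cases it works. But the protocol does not say that Section 8.1 adds to Section 5.2 or that the stricter text governs. Case (e) needs more: the statement in Section 8.1 that such patients are eligible has to be read as subject to Section 5.2, which it does not say.

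**Sites are directed to Section 8.1.** The brain-scan row and footnote i both point there, and Section 4.1.1 requires all screening results to be reviewed before enrolment. This stands: the rule is not hidden. The eligibility row still points only to Section 5.

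**The wording on known lesions is softer.** Section 8.1 says they should be stable, whereas it says outright that new metastases exclude. This stands, and it is why case (b) is described as not meeting a condition and not as an outright exclusion.

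**Few patients can reach the conflict.** Screening brain scans need known or suspected CNS disease or neurological symptoms. Where symptoms prompt the scan and a new metastasis explains them, both sections exclude the patient. This also stands.

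**General exclusion 30** covers conditions that might confound the results. It does not name CNS lesions and leaves the matter to judgement, so it does not settle the question.

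**Conclusion.** The inconsistency is real and should be corrected, but it is narrow. For Cohorts 1 to 5, Sections 5.2 and 8.1 give different answers for an asymptomatic metastasis new at screening, for a known untreated asymptomatic lesion not shown stable for six weeks, and, in the opposite direction, for a symptomatic lesion shown stable. The number of patients is unknown and probably small. That last judgement rests on the limited triggers for brain imaging, not on a figure in the documents.

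A reader might infer more than the texts support:
- **That Section 8.1 bars all untreated lesions.** It does not. An untreated asymptomatic lesion shown stable for six weeks passes both sections.
- **That 170 of 200 participants are affected.** That is the planned size of the cohorts under the wording, not a count of conflicting cases.
- **That the primary endpoint is biased through early progression.** The documents do not support this. Under the RECIST rules in Section 10.6.1, a lesion present at baseline is recorded as target or non-target disease and does not later count as a new lesion.
- **That the absence of a DMC makes matters worse.** Whether two eligibility texts agree does not depend on a monitoring committee.
- **That the scan triggers conflict in substance.** The wording differs, but footnote i defers to Section 8.1, and suspected lesions would ordinarily take in patients with neurological symptoms.

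**What to change.** Reconcile the passages. State a single CNS eligibility rule in exclusions 103, 203, 304, 402 and 502 that deals explicitly with new lesions, known untreated lesions and treated lesions, and says how symptoms count in each. Which rule applies is for the sponsor to decide. Replace the eligibility sentences in Section 8.1 with a cross-reference to Section 5.2, and align the scan-trigger wording in footnote i with Section 8.1.

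The cost is amendment wording and an updated eligibility checklist. No extra scans are needed if the existing trigger in Section 8.1 is kept.

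SAP version 3.0 covers the final analysis once all participants have discontinued, so an amendment may no longer affect who is enrolled. If enrolment has ended, state in the study report which rule governed CNS eligibility and classify CNS-related eligibility deviations by that rule alone. SAP Section 6.4 refers to SAP version 2.0 for protocol deviations. That version is not among the documents reviewed, so it should be checked for any existing classification rule. This step costs a review of the screening CNS findings already recorded for Cohorts 1 to 5 and a short statement in the report.
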